## 10.5 Sterilization

### 10.5.1 Ring/Band (Model 638R/638B)

The ring and band are provided sterile (ethylene oxide) on the holder and must not be resterilized. Rings and bands that have been damaged or contaminated from patient contact should not be used.

## 11 REGISTRATION INFORMATION

**Note:** Patient registration does not apply in countries where patient privacy laws conflict with providing patient information, including countries from the EU.

A patient registration form is included in each device package. After implantation, please complete all requested information.

The serial number may be found on the package and on the identification tag attached to the device. Return the original form to the Medtronic address indicated on the form and provide the temporary identification card to the patient prior to discharge.

## 12 DISCLAIMER OF WARRANTIES

### THE FOLLOWING DISCLAIMER OF WARRANTY APPLIES TO UNITED STATES CUSTOMERS ONLY:

The exclusions and limitations set out above are not intended to, and should not be construed so as to, contravene mandatory provisions of applicable law. If any part or term of this Disclaimer of Warranty is held by any court of competent jurisdiction to be illegal, unenforceable, or in conflict with applicable law, the validity of the remaining portion of the Disclaimer of Warranty shall not be affected, and all rights and obligations shall be construed and enforced as if this Disclaimer of Warranty did not contain the particular part or term held to be invalid.

#### DISCLAIMER OF WARRANTY

ALTHOUGH THE CG FUTURE® 638R/638B ANNULOPLASTY RING/BAND, THE CG FUTURE® 7638 RING/BAND SIZER SET, AND THE MEDTRONIC 7615 ANNULOPLASTY HANDLE, HEREAFTER REFERRED TO AS "PRODUCT," HAVE BEEN MANUFACTURED UNDER

CAREFULLY CONTROLLED CONDITIONS, MEDTRONIC HAS NO CONTROL OVER THE CONDITIONS UNDER WHICH THIS PRODUCT IS USED. MEDTRONIC, THEREFORE, DISCLAIMS ALL WARRANTIES, BOTH EXPRESS AND IMPLIED, WITH RESPECT TO THE PRODUCT, INCLUDING, BUT NOT LIMITED TO, ANY IMPLIED WARRANTY OF MERCHANTABILITY OR FITNESS FOR A PARTICULAR PURPOSE. MEDTRONIC SHALL NOT BE LIABLE TO ANY PERSON OR ENTITY FOR ANY MEDICAL EXPENSES OR ANY DIRECT, INCIDENTAL, OR

CONSEQUENTIAL DAMAGES CAUSED BY ANY USE, DEFECT, FAILURE, OR MALFUNCTION OF THE PRODUCT, WHETHER A CLAIM FOR SUCH DAMAGES IS BASED UPON WARRANTY, CONTRACT, TORT, OR OTHERWISE.

NO PERSON HAS ANY AUTHORITY TO BIND MEDTRONIC TO ANY REPRESENTATION OR WARRANTY WITH RESPECT TO THE PRODUCT.

### THE FOLLOWING DISCLAIMER OF WARRANTY APPLIES TO CUSTOMERS OUTSIDE THE UNITED STATES:

The exclusions and limitations set out above are not intended to, and should not be construed so as to, contravene mandatory provisions of applicable law. If any part or term of this Disclaimer of Warranty is held to be illegal, unenforceable, or in conflict with applicable law by a court of competent jurisdiction, the validity of the remaining portions of this Disclaimer of Warranty shall not be affected, and all rights and

# PRESERVE-Mitral Clinical Investigation Plan

MDT16016SUR002

Version 1.0, dated 10-APR-2017

Page 55 of 58

Medtronic

obligations shall be construed and enforced as if this Disclaimer of Warranty did not contain the particular part or term held to be invalid.

## DISCLAIMER OF WARRANTY

ALTHOUGH THE CG FUTURE® 638R/638B ANNULOPLASTY RING/BAND, THE CG FUTURE® 7638 RING/BAND SIZER SET, AND THE MEDTRONIC 7615 ANNULOPLASTY HANDLE, HEREAFTER REFERRED TO AS "PRODUCT," HAVE BEEN CAREFULLY DESIGNED, MANUFACTURED, AND TESTED PRIOR TO SALE, THE PRODUCT MAY FAIL TO PERFORM ITS INTENDED FUNCTION SATISFACTORILY FOR A VARIETY OF REASONS. THE WARNINGS CONTAINED IN THE PRODUCT LABELING PROVIDE MORE DETAILED INFORMATION AND ARE CONSIDERED AN INTEGRAL PART OF THIS DISCLAIMER OF WARRANTY. MEDTRONIC, THEREFORE, DISCLAIMS ALL WARRANTIES, BOTH EXPRESS AND IMPLIED, WITH RESPECT TO THE PRODUCT. MEDTRONIC SHALL NOT BE LIABLE FOR ANY INCIDENTAL OR CONSEQUENTIAL DAMAGES CAUSED BY ANY USE, DEFECT, OR FAILURE OF THE PRODUCT, WHETHER THE CLAIM IS BASED ON WARRANTY, CONTRACT, TORT, OR OTHERWISE.

Figure 1

[figure not shown]
[figure not shown]

Figure 2

Figure 3

**Medtronic Confidential**

This document is electronically controlled

056-F275, v3.0 Clinical Investigation Plan Template

Figure 6

Figure 4

[figure not shown]
[figure not shown]
[figure not shown]
[figure not shown]
[figure not shown]
[figure not shown]

Figure 7

Figure 5

# PRESERVE-Mitral Clinical Investigation Plan

MDT16016SUR002

Version 1.0, dated 10-APR-2017

Page 57 of 58

Medtronic

Figure 8

[figure not shown]
[figure not shown]

Figure 9

[figure not shown]
[figure not shown]

Figure 10

[figure not shown]
[figure not shown]
[figure not shown]
[figure not shown]

Figure 11

[figure not shown]
[figure not shown]

**Medtronic Confidential**

This document is electronically controlled

056-F275, v3.0 Clinical Investigation Plan Template

Figure 12

## 18. Version History

Version	Summary of Changes	Author(s)/Title
1.0	

Not Applicable, New Document

	[name], Clinical Study Manager [name], Clinical Study Manager

## 1. Version History

Version	Summary of Changes	Author(s)/Title
1.0	

Not Applicable, New Document

	[name], Principal Statistician
2.0	

Revised analysis set for primary and secondary endpoints to Successfully Implanted subjects.

Revised analysis method for new onset of atrial fibrillation to Kaplan-Meier analysis.

Added specification on the time point at which a subject is deemed to have an attempted implant.

Added specification on the standard error estimator for the Kaplan-Meier analyses.

Last follow-up date definition was revised for subjects with exit reason of lost to follow-up.

Revised Section 7.6 to include Enrolled and Successfully Implanted cohorts in reporting of demographic and other baseline characteristics.

Revised Section 7.7 to include Attempted Implant and Successfully Implanted cohorts in reporting of procedural characteristics.

Added subgroup analyses for the primary and selected secondary endpoints.

	[name], Principal Statistician

## 2. List of Abbreviations and Definitions of Terms

Abbreviation	Definition
ACC	American College of Cardiology
AE	Adverse Event
AF	Atrial Fibrillation
AHA	American Hospital Association
ASE	American Society of Echocardiography
CIP	Clinical Investigation Plan
CRF	Case Report Form
CSH	Medtronic Coronary and Structural Heart
CVD	Cardiovascular Disease
ECG	Electrocardiogram/Electrocardiography
eCRF	Electronic Case Report Form
IFU	Instructions For Use
LAR	Legally Authorized Representative
MR	Mitral Regurgitation
NYHA	New York Heart Association
PRESERVE – MITRAL	Prospective REgistry to Study Clinical OutcomEs of Repair of Mitral ValvEs in South Asia
SAP	Statistical Analysis Plan
UADE	Unanticipated Adverse Device Effect

## 3. Introduction

Cardiovascular Diseases (CVD) are the leading cause of mortality in India, contributing to 25% of all mortality in the country. The Global Burden of Disease study estimate of age-standardized CVD death rate of 272 per 100,000 population in India is higher than the global average of 235 per 100,000 population [1].

One of the important pathologies seen in patients with cardiovascular disease is mitral valve regurgitation and insufficiency. Patients might suffer from different types of mitral valve dysfunction leading to different levels of regurgitation.

Mitral valve repair is established as a procedure to alleviate mitral valvular insufficiency/stenosis. The pathophysiology of mitral valve insufficiency can be ischemic, rheumatic, degenerative, congenital, infective, myxomatous, etc.

Mitral valve repair may lead to better outcomes as compared to replacement. Western studies on mitral valve repair have typically focused on patients with ischemic pathophysiology. Current ACC/AHA guidelines [2] state that mitral valve repair is recommended in preference to mitral valve replacement in certain patients with chronic severe primary MR limited to posterior leaflet, or involving the anterior leaflet or both leaflets when a successful and durable repair can be accomplished. Concomitant repair is indicated for patients with chronic severe primary MR if they undergo cardiac surgery.

Despite the guidelines, there may be local and regional differences in the standard practice in different geographies. While there are some Indian studies that have looked into mitral valve repair [3], [4], [5], there is still a need to gather more local evidence on clinical outcomes at long term follow up (12 months). The significant proportion of mitral valve repair patients in India have rheumatic disease. Mitral valve repair is more technically challenging in this population, and is associated with higher failure rate.

Given this background, it is clear that the significant body of evidence for mitral valve annuloplasty from the west may not give a realistic picture of patients undergoing the same procedure in South Asia. Due to the difference in disease pathophysiology, the significant population of patients with rheumatic disease and differing surgical practice, there is a need to conduct a geography-specific study to understand the clinical outcome of patients undergoing mitral valve annuloplasty in the region. PRESERVE-Mitral, a prospective registry to study long term performance of annuloplasty systems is thus proposed to document clinical outcomes, physician practice and report on outcomes in these patients.

There is limited local evidence on mitral repair products in South Asia and a prospective post-market registry will provide real world data on clinical outcomes.

## **4. Study Objectives**

### **4.1 Primary Objective(s)**

The objective of this registry is to gather data on the clinical outcomes of Medtronic mitral repair products (Profile 3D™ or CG Future® Annuloplasty systems, which include Profile 3D Ring, CG Future Ring and CG Future Band) in the approved intended use up to 12 months from the day of procedure.

### **4.2 Secondary Objective(s)**

Characterize the demographics of the patients undergoing mitral valve repair using annuloplasty systems in South Asia, and assess the functional and procedural outcomes of the procedure.

## **5. Investigation Plan**

### **5.1 Study Design**

PRESERVE-Mitral is a prospective non-randomized non-interventional post-market registry. A total of 200 patients who are eligible and who are intended to be implanted with a Profile 3D™ or CG Future® Annuloplasty system in the surgical repair procedure will be included in the study.

The subjects will be evaluated at discharge for evaluation of procedural success and subsequently followed up as per standard-of-care at the site from 3-6 months (90 days to 210 days) post procedure and at 12 months (365 days +/- 30 days) post procedure for assessment of longer-term outcome at which time subjects will also exit the study. Echo images will be evaluated pre-implant, intra-op, discharge and during follow ups, according to the standard routine in the center.

## 5.2 Selection of Subjects

### 5.2.1 Study Population

The patient population includes all patients suffering from mitral valve disease, indicated for a mitral valve repair procedure, either as a stand-alone procedure or concomitant to another procedure (for example, coronary artery bypass grafting, tricuspid valve repair, treatment of atrial fibrillation, etc. but excluding patients undergoing aortic valve replacement) and for which the surgeon considers the implantation of a Profile 3D™ or CG Future® Annuloplasty system most appropriate to reconstruct the regurgitant valve.

### 5.2.2 Subject Enrollment

A subject is considered enrolled in this study at the time at which he/she signed the Patient Informed Consent Form.

### 5.2.3 Inclusion Criteria

1. Patients with valvular insufficiency and/or stenosis and indicated for the reconstruction and/or remodeling of pathological mitral valves with Profile 3D™ or CG Future® Annuloplasty systems.
2. Indications and contraindications provided in the product Instructions for Use (IFU).
3. Subject is 18 years of age or older.
4. The patient or his/her Legally Authorized Representative (LAR) has been informed about the nature of the registry and the patient informed consent for study participation has been obtained prior to performing any study-related procedures from the subject or LAR, as per applicable local requirements.

### 5.2.4 Exclusion Criteria

1. Contraindications as per IFU:
  - a. Heavily calcified valves;
  - b. Valvular retraction with severely reduced mobility;
  - c. Active bacterial endocarditis.
2. Aortic valve replacement as concomitant procedure.
3. Already participating in another clinical study, possibly leading to bias and jeopardizing the scientific appropriate assessment of the study endpoints.

## 6. Determination of Sample Size

The sample size of 200 subjects who are eligible and intended to be implanted with a Profile 3D™ or CG Future® Annuloplasty system in the surgical repair procedure is adequate and appropriate for the evaluation of local evidence and obtaining real world data on clinical outcomes following implantation of these two products. This sample size was not statistically derived as this is not a hypothesis driven study.

## 7. Statistical Methods

### 7.1 Study Subjects

#### 7.1.1 Disposition of Subjects

Subject disposition will be summarized, including the number of subjects enrolled, attempted implant, successfully implanted, died, explanted, withdrawn, lost to follow-up, and completed each visit during the study.

#### 7.1.2 Clinical Investigation Plan (CIP) Deviations

Protocol violations (study deviations) will be reported to Medtronic throughout the study by each site and identified through monitoring activities. CIP deviations will be summarized.

#### 7.1.3 Analysis Sets

There are three analysis sets defined for this study. Analysis sets used for each objective are defined in the corresponding objective section. The primary analysis set is the Successfully Implanted analysis set.

- Enrolled analysis set: Composed of all subjects who signed the Patient Informed Consent Form. Time zero begins on the date of informed consent.
- Attempted Implant analysis set (AT): Composed of all enrolled subjects who were attempted for a Profile 3D™ or CG Future® Annuloplasty system implantation. A subject with one or more attempts of the Medtronic study device recorded on the procedure case report form (CRF) is considered as implant attempted. Time zero begins on the date of the first attempted procedure.
- Successfully Implanted analysis set (IMP): Composed of all AT subjects who had either a Profile 3D™ or CG Future® Annuloplasty system implanted successfully. Time zero begins on the date of implant procedure.

All data collected from enrolled, attempted implant, and successfully implanted subjects will be utilized in the analyses as appropriate. Analyses of the primary and secondary endpoints will be descriptive, and no statistical hypothesis tests will be performed.

### 7.2 General Methodology

Descriptive statistics will be used to report study data. For continuous variables (e.g. age), the mean, median, standard deviation, minimum, maximum, and first and third quartiles will be presented. For categorical variables, the number and percentage of subjects in the category of interest will be presented. For time to event data, Kaplan-Meier analyses of event or event-free rates at discharge, 6 and 12 months will be presented. For these analyses, the time points will correspond to 7 days, 183 days and 365 days post implantation respectively. At each time point with data, the product limit estimate of the event or event-free rates, and the loglog transformed 95% confidence interval using the Peto standard error will be presented. For subjects without an event, the date of censoring will be the latest date of all follow-up visits (including phone and/or mail correspondence), assessments, events (including death) and study exits. For subjects whose exit reason is lost to follow-up, the last follow-up date will be the latest date of the follow-up visits (including phone and/or mail correspondence), assessments and events.

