Stroke is defined as an acute episode of focal or global neurological dysfunction caused by brain, spinal cord, or retinal vascular injury as a result of hemorrhage or infarction, where the neurological dysfunction lasts for greater than 24 hours. The occurrence of stroke will be evaluated at 6 months and 12 months post procedure.

- New onset of Atrial Fibrillation, as evaluated through follow up ECG at discharge, first follow up (3-6 months) and at second follow up (12 months)

New onset of AF is defined as when the subject did not present with prior history of AF at baseline nor was AF detected at baseline visit, but AF did manifest post procedure and was either diagnosed during the study visits (discharge, 3-6 months or 12 months visit) or was otherwise diagnosed during the duration of subject participation in the study. The incidence of new onset AF will be evaluated at discharge, first follow up (3-6 months) and at second follow up (12 months).

- Number of attempts required for procedural success, and bypass time as a measure of procedural complexity, as measured by standard operating room procedures at the site.

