## 9.11. Subject Withdrawal or Discontinuation

All subjects will be encouraged to remain in the registry through the last follow-up visit at 12 months. Subjects who discontinue participation prematurely after attempted implant will be included in the analysis of results (as appropriate) but they will not be replaced in the enrollment of total study subjects. If a study subject is discontinued from the study early, the reason for discontinuation should be documented in the subject file and a Study Exit eCRF must be completed. If discontinuation is because of safety concerns, the subject shall be asked to be followed for collection of ongoing safety data outside the study. Any data collected after the exit date will not be analyzed as part of the study.

In case the subject undergoes device explant, the subject will be exited from the study.

The subjects will be exited from the study following their 12 month follow up visit. This 12 month visit will be primarily conducted via in-office visit and has a window period of additional 1 month, up to day 395 post implant. All adverse event information will be collected and reported during this follow up visit, as per timelines described above in section 11.2; subjects will be considered exited from the study on completion of their 12 month visit or when they are considered lost to follow up (after three failed attempts are made to contact the subjects).

The investigating site and Sponsor will make every effort to have all subjects complete the follow up visit schedule. A subject will not be considered lost-to-follow-up unless all efforts to obtain compliance are unsuccessful. At a minimum, the effort to obtain follow-up information must include three attempts to make contact via telephone and if contact via phone is not successful, a traceable letter from the Investigator must be sent to the subject's last known address. Should both telephone and mail efforts to contact the subject be unsuccessful, the subject's primary physician should be contacted. Subjects will then be deemed lost to follow up. All contact efforts to obtain follow-up must be documented in the subject's medical records.

If a subject discontinues the study at any time, is withdrawn from the study early, or completes all protocol required follow-up they should then be followed per the local standard of care for their condition.

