**7.9.9 Secondary Endpoint #7**

New onset of atrial fibrillation (AF), as evaluated through follow up ECG at discharge, first follow up (3-6 months) and at second follow up (12 months), as well as on the AE form.

Hypothesis/Decision criteria:

No specific hypotheses or pass/fail criteria have been set. The analysis will be descriptive and no statistical hypothesis test will be performed.

Endpoint Definition/Parameters to Be Estimated:

New onset of AF is defined as when the subject did not present with prior history of AF at baseline nor was AF detected at baseline visit, but AF did manifest post procedure and was either diagnosed during the study visits (discharge, 3-6 months or 12 months visit) or was otherwise diagnosed during the duration of subject participation in the study.

Data Collection and Analysis Dataset:

Data will be collected on a DISCHARGE/FOLLOW UP (SV) CRF or an AE CRF.

This objective will be analyzed for the Successfully Implanted (IMP) cohort.

Analysis Method:

A Kaplan-Meier analysis will be performed.

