## **7.12 Changes to Planned Analysis**

Analysis set defined in the CIP for the primary and secondary endpoints is changed to the Successfully Implanted set in order to align with other surgical valve studies.

New onset of atrial fibrillation will be evaluated using Kaplan-Meier method instead of percent of subjects as described in the CIP in order to incorporate subject censoring in the course of the study. Atrial fibrillation identified on the post-procedural ECG or AE forms will be included in the analysis.

Changes to V1.0 of the SAP include: Baseline data will be presented for the Enrolled and Successfully Implanted cohorts, and procedural data will be presented for the Attempted Implant and Successfully Implanted cohorts. As one of the objectives of the registry is to characterize subjects who are considered eligible for mitral valve repair in South Asia, analyzing baseline and procedural characteristics on these analysis cohorts will cover the populations of interest.

Sub-group analyses will be performed on the Successfully Implanted subjects with CG Future Band, CG Future Ring and Profile 3D Ring respectively for the primary and selected secondary endpoints.

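### The day-365 Kaplan-Meier reading of new-onset AF misstates AF first found at the 12-month ECG, because that visit falls on days 335-395 and also ends follow-up

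*Combined protocol and SAP*

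**What the plan says.** - **Reading days.** SAP 7.2, on all time-to-event summaries at discharge, 6 and 12 months: "For these analyses, the time points will correspond to 7 days, 183 days and 365 days post implantation respectively".
- **Censoring.** SAP 7.2: "For subjects without an event, the date of censoring will be the latest date of all follow-up visits", along with assessments, events and study exits. For an AF-free subject who completes the study, that is normally the 12-month visit.
- **The 12-month visit.** SAP 5.1 places it "at 12 months (365 days +/- 30 days) post procedure for assessment of longer-term outcome at which time subjects will also exit the study". CIP 9.11 agrees on exit ("subjects will be considered exited from the study on completion of their 12 month visit") but words the window differently: the visit "has a window period of additional 1 month, up to day 395 post implant".
- **AF endpoint.** CIP 5.2.2 asks for incidence at the discharge, 3-6 month and 12-month visits. CIP 13.6 item 7 planned a number and percent at each. SAP 7.9.9 now says "A Kaplan-Meier analysis will be performed", and SAP 7.12 records the change: "New onset of atrial fibrillation will be evaluated using Kaplan-Meier method instead of percent of subjects as described in the CIP", in order to allow for censoring. AF seen on a post-procedural ECG counts as an event, as does AF on an AE form or otherwise diagnosed during participation.

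Neither document maps visit findings to a nominal day, specifies an interval-censored method, or says what date AF first seen on a visit ECG receives.

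**The concern.** Kaplan-Meier assumes that an event has its own date and that censoring is unrelated to it. Stroke, heart-failure admission and death have such dates. AF first seen on the 12-month ECG does not: it is dated by the appointment, and the same appointment censors everyone found AF-free. Two distortions follow.

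1. AF found on an in-window ECG on days 366-395 lies beyond the reading day and is left out of the 12-month rate, although the CIP counts it at the 12-month visit.
2. From day 335 the AF-free subjects already seen have left the risk set, so AF found at a later visit up to day 365 is divided by a shrinking denominator and over-weighted.

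The result is a 12-month AF rate that depends partly on when visits are booked. The study is descriptive, so no test is affected. The rate and its interval are the whole output for this endpoint, however, and the interval would not reveal the problem.

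**Working it through.** The documents give no AF rate or precision figure to reproduce, and the sample size of 200 is stated as not statistically derived.

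**Inputs from the documents.** Reading day 365 and censoring at last contact (SAP 7.2); visit on days 335-395 with exit at the visit (SAP 5.1, CIP 9.11); AF on the visit ECG counts (SAP 7.12).

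**Assumptions.** Visit-detected AF is dated to the ECG. A share p of subjects who reach the visit AF-free have AF first found there; p = 3%, with 5% as a variation. F is the share of 12-month visits on or before day 365. Early AF is 0% or 15%. AF yield does not depend on visit day.

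**Formula.** When a fraction F of visits has occurred, the risk set is 1 - F of those who entered the window. Events arrive at rate p dF, so the cumulative hazard is -p ln(1 - F). The contribution at day 365 is therefore 1 - (1 - F)^p, whereas the intended value is p.

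**Contribution with p = 3% (true value 3.0 points).**

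| F | Calculation | Contribution (points) |
|---|---|---|
| 0% | nothing observed by day 365 | 0.0 |
| 25% | 1 - 0.75^0.03 | 0.9 |
| 50% | 1 - 0.50^0.03 | 2.1 |
| 75% | 1 - 0.25^0.03 | 4.1 |
| 90% | 1 - 0.10^0.03 | 6.7 |
| 100% | 1 - product over k = 1 to 31 of (1 - 0.03/k) | 11.4 |

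The last row needs the discrete form, with visits spread evenly over the 31 days 335-365. Simulating 130 AF-free subjects gave 0.0, 0.9, 2.1, 4.0, 6.4 and about 11 to 12. With p = 5%, the 50% row is 1 - 0.50^0.05 = 3.4 points, and the extremes are 0 and 18.4.

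**Total rate with 15% early AF and p = 3%.** The true value is 1 - 0.85 x 0.97 = 17.5%. The reading is 1 - 0.85 x (1 - F)^0.03:
- F = 25%: 15.7%
- F = 50%: 16.8%
- F = 75%: 18.5%
- F = 0% and 100%: 15.0% and 24.7%

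Simulating 150 subjects gave the same values to within about 0.1 point.

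**Reading at day 395 instead.** This is no remedy, because the risk set is nearly empty by then. In simulation, a 3% yield with visits split evenly around day 365 read about 13 points.

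**Assigning the 12-month findings and exits to day 365.** All completers are then at risk together, and the increment is events divided by completers. Simulation returned 3.0 points (17.5-17.6% with early AF) under every booking pattern.

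**The two window wordings.** If CIP 9.11 means days 365-395, with visits spread evenly over those 31 days, then F = 1/31 and the contribution is 1 - (30/31)^0.03 = 0.1 point. Almost all AF found at the 12-month ECG would be left out.

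**The case against.** The strongest reply is that the effect is confined and may be small. AF counts whenever it is diagnosed during participation. AF dated earlier, from an AE form or from the discharge or 3-6 month ECG, is not distorted at 12 months. If early AF dominates, the total moves by less than 2 points for 25-75% shares. The extremes require nearly every visit, across 10 centres following local practice, to fall on one side of day 365. This is also a descriptive secondary endpoint with no pass/fail criterion. All of that stands and limits the size. It does not remove the mechanism, which follows from the plan as written.

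Four stronger readings are tempting, and the documents do not support them.

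- *Booking matters more than AF itself.* That would need most new AF to be first seen at the 12-month ECG, or extreme booking. The documents do not give the split by detection time.
- *The 12-month AF endpoint is not estimated.* It is estimated, with a bias in one component.
- *Sites will report different rates because of their booking habits.* No by-site AF rate is planned; SAP 7.9.9 analyses the whole implanted cohort.
- *The 6-month estimate loses AF in the same way.* AF found on days 184-210 misses the day-183 reading, but those subjects remain in follow-up, so it is deferred to the 12-month estimate.

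The ECG-date assumption is also open to challenge. CIP 9.9.5 records adverse events since the last visit on an AE form, so some AF noted at 12 months may carry an earlier onset date. Against that, CIP 9.8 limits collection through the study to serious events, so non-serious AF may surface only on a visit ECG.

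**Conclusion.** The concern holds for AF first detected at the 12-month ECG. As written, the plan omits such AF when the in-window visit falls after day 365 and over-weights it when the visit falls before. A true 3-point contribution reads as 0.9 to 4.1 points for 25-75% of visits by day 365, and 0 to about 11.4 at the extremes. With 15% early AF, a true 17.5% reads as 15.7-18.5%, and 15.0-24.7% at the extremes. The mechanism and direction rest on the documents. The sizes rest on the assumed yield, early-AF rate, booking pattern and ECG dating, none of which the documents supply. It should be corrected, since the correction needs no new data.

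**What to change.** 1. In SAP 7.9.9, for the 12-month estimate, assign to nominal day 365 both AF first found on the in-window 12-month visit ECG and the censoring of AF-free subjects who complete that visit. Keep actual dates for AF with its own onset date on the AE form, and state which source prevails when both record the same episode.
2. Do not map the 3-6 month visit to day 183. That visit may occur as early as day 90, and a subject seen AF-free then and later lost would gain 183 - 90 = 93 unobserved AF-free days.
3. Report the CIP 13.6 item 7 number and percent by visit, with the number assessed, as a supplement. This keeps the SAP's reason for using Kaplan-Meier and gives a figure that does not depend on visit day.
4. Reconcile the window wording in CIP 9.11 with 365 +/- 30 days.

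**Cost.** SAP wording, one derived-date rule and one extra table. AF found at the 12-month visit is timed to the nominal day instead of the ECG date, a shift of at most 30 days. AF-free subjects seen from day 335 are likewise carried up to 30 days beyond their last observation.
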